10.3.3 Participants' characteristics and potential confounders/risk factors

The variables presented in Table 6 will be considered to describe the cohorts' characteristics (objective 5), as selection criteria or as adjustment variables for confounding control. The final choice of characteristics, risk factors and confounders will depend on the availability of data (e.g., malignancy family history) and clinical relevance. After feasibility assessment, ethnicity was excluded as a covariate since it was not available in any of the data sources (Table 26). Specific definitions will be presented in detail in the SAP.

At baseline, the variables presented in Table 6, will be considered to create the PS, since they may influence the decision of prescribing anifrolumab or other SLE SOC drugs and are considered potential risk factors for each outcome. Confounding variables will be retrieved at index date or in the look-back period as presented in Figure 2 and Figure 3.

In the following sections, specific confounders for malignancies will be presented, followed by serious infections confounders and SLE disease severity and activity. A summary of the variables for each cohort is presented in Table 6.

	Study	cohort
	Serious infections	Malignancies
Demographic characteristics		
Cohort entry year	✓	✓
Age	✓	✓
Sex	✓	✓
Socioeconomic status (including education)	✓	✓
Lifestyle characteristics		
Smoking	✓	✓
Alcohol/substance abuse	✓	✓
Height, weight, or body mass index (kg/m ²)	✓	✓
General Medical History		
Comorbidities relevant for SLE patients (Table 20)	✓	✓
Malignancy family history		✓
Procedures with radiation exposure		✓
Prior virus/infections (risk factors for malignancies) (Table 22)		✓
Previous infection (serious and non-serious infection)	✓	
Vaccines and passive immunity drugs (Table 23)	✓	
Comedication [polypharmacy] (Table 24)	✓	✓
SLE disease history and profile		
Disease duration, months (time from diagnosis to study entry)	✓	✓
Disease severity components	~	✓
Disease activity	✓	✓
SLE standard of care (Table 14)	✓	✓

Table 6 Participant characteri	stics and confounding	variables for	each study cohort:
malignancy and serious infection	7		-

Abbreviations: SLE, systemic lupus erythematosus.

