10.3.3.1 Potential confounders for the malignancy cohort

For the analysis of malignancies, potential confounders include demographics and lifestyle characteristics (as presented in Table 6), SLE history (including SLE severity, activity as detailed below) and other clinical characteristics. Some infections may be important risk factors for specific types of malignancies [6, 63] (Table 22), such as Human Papillomavirus (HPV) infection and the risk associated with cervical cancer [84] or the emergence of the oncogenic Epstein-Barr virus. HPV vaccine will be considered as reducing the risk of cervical, oropharyngeal, and anal cancer occurrence.

⁷Some data sources may not have available some of the relevant variables.

Comorbidities recognised as risk factors for cancer development will be considered, namely cardiovascular diseases [44, 45], diabetes [94], liver disease [87], kidney disease [86], chronic respiratory disease [25, 55], among others (Table 20). Likewise, several drugs have been associated with changes in the risk of cancer and will be included as covariates, namely antidiabetics [91], antihypertensives [20], antihrombotic agents [43, 53] and other recognised carcinogenic drugs (Table 24).

Furthermore, increased inflammatory activity is purported to be associated with malignancy risk. In addition to considering SLE severity and activity, other comorbidities may increase inflammatory status, namely other autoimmune diseases (excluding SLE), acquired immunodeficiencies, and chronic infections. Exposure to specific SLE drugs, such as prednisolone, cyclophosphamide, rituximab, azathioprine or cyclosporin, has also been purported to be associated with cancer development [3, 11, 100]. Adjustment for prior use of cyclophosphamide or rituximab are already taken into account when controlling the SLE severity as these drugs are used to define severe SLE. Within the group of other immunosuppressants, recognised carcinogenic drugs will be considered separately.

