	N30.8, N34.0, N39.0, N41.2, N43.1, N45, N48.2, N61, N70-N74, N75.1,
	O23, O26.4, O41.1, O75.3, O85, O86, O88.3, O91, O98, R65.0, R65.1,
	B34.2, B97.2, J12.81, J12.82, U07.1, U07.2, U10

Table 16 Exemplar code list of serious infections (composite outcome)

Abbreviations: ICD-10, international statistical classification of diseases tenth revision

Group	Subgroup	Clinical Code Description	ICD-10
	S-1	Salmonella sepsis	A02.1
	Salmonella	Localized salmonella infections	A02.2
		Respiratory tuberculosis, bacteriologically and histologically confirmed	A15
	Tuberculosis	Respiratory tuberculosis, not confirmed bacteriologically or histologically	A16
		Tuberculosis of nervous system	A17
		Tuberculosis of other organs	A18
		Miliary tuberculosis	A19
		indeterminate leprosy	A30.0
		Tuberculoid leprosy	A30.1
		Borderline tuberculoid leprosy	A30.2
	_	Borderline leprosy	A30.3
	Leprosy	Borderline lepromatous leprosy	A30.4
		Lepromatous leprosy	A30.5
		Other forms of leprosy	A30.8
		Leprosy, unspecified	A30.9
Bacterial		Pulmonary mycobacterial infection	A31.0
	Infection due to	Cutaneous mycobacterial infection	A31.1
	other mycobacteria	Other mycobacterial infections	A31.8
		Mycobacterial infection, unspecified	A31.9
	Listeriosis	Listerial meningitis and meningoencephalitis	A32.1
		Listerial sepsis	A32.7
		Other forms of listeriosis	A32.8
	Nocardiosis	Pulmonary nocardiosis	A43.0
		Cutaneous nocardiosis	A43.1
		Other forms of nocardiosis	A43.8
		Nocardiosis, unspecified	A43.9
	Systemic bartonellosis	Systemic bartonellosis	A44.0
		Legionnaires disease	A48.1
	Legionnaires disease	Nonpneumonic Legionnaires disease [Pontiac fever]	A48.2
	Vibriosis (invasive disease due to Vibrio vulnificus)	sis (invasive e due to Vibrio Vibrio vulnificus as the cause of diseases classified to other chapters	
	Progressive multifocal leukoencephalopathy	Progressive multifocal leukoencephalopathy	A81.2
Viral		Herpesviral gingivostomatitis and pharyngotonsillitis	B00.2
	Herpes simplex	Herpesviral meningitis	B00.3
		Herpesviral encephalitis	B00.4

Table 17 Exemplar code list of opportunistic serious infections

Group	Subgroup	Clinical Code Description	ICD-10
		Herpesviral ocular disease	B00.5
		Disseminated herpesviral disease	B00.7
		Zoster encephalitis	B02.0
		Zoster meningitis	B02.1
		Zoster with other nervous system involvement	B02.2
	Herpes Zoster	Zoster ocular disease	B02.3
		Disseminated zoster	B02.7
		Zoster with other complications	B02.8
		Zoster without complication	B02.9

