	Pleuritis [51]	A15.6, A15.7, A16.5, A16.7
	Thrombocytopenia [51]	D69.6, D69.5, D69.4
Other comorbidities	Autoimmune diseases excluding SLE (e.g., rheumatological, inflammatory bowel disease and multiple sclerosis) [101] Immunodeficiencies (excluding congenital and HIV) [30]	L40, I73.0, M15.0, M35.0, K50, K51, G35 D80-D89
	Cardiovascular diseases (atrial fibrillation, coronary artery disease, hypertension) [46, 67, 81]	I48, I25.1, I10-I15
	Chronic respiratory diseases [30, 35, 67, 101]	J40-J47
	Gastrointestinal conditions (e.g., peptic ulcer disease, gastro- oesophageal reflux disease, dyspepsia, helicobacter pylori infection, Barrett's oesophagus, gastritis and duodenitis, chronic pancreas disease, chronic liver disease, gallstones)	K21, K22.7, K25-K29, K30, K76.9, K80-K82, K86, B98.0

Abbreviations: HIV, human immunodeficiency virus; ICD-10, international statistical classification of diseases tenth revision.

*Three variables were removed from the index because they are exclusion or censoring criteria: HIV, metastatic disease, any malignancy.

Table 21 Exemplar code list for SLE-related comorbidities (SLE severity and activity algorithms)¹¹

	Group	Conditions	ICD-10 codes
Moderate comorbid	Cardiovascular	Haemolytic anaemia	D55-D59
conditions	cardiorespiratory system	Myocarditis	I40
		Pericarditis	I30
		Pleurisy/pleural effusion	J90 J91
		Vasculitis (excluding aortitis)	M05.2
	Hepatic and	Acute pancreatitis	K85
	gastrointestinal	Hepatitis (non-viral)	K72.0
		Lupus enteritis/colitis	
	Musculoskeletal	Avascular ischaemic necrosis of bone	M87
	Neurological	Demyelinating syndrome/acute inflammatory demyelinating	G36-G37
		polyradiculoneuropathy	
		Mononeuropathy/polyneuropathy	G56-G64
		Myelopathy	G99.2
		Pseudotumor cerebri	G93.2
		Seizure	R56.8
	Renal	Nephritis	N10, N11
		Renal impairment (other than nephritis or end-stage renal disease)	S37.0, N18 (excl. N18.5)
	Ocular	Chorioretinitis	H30.9
		Episcleritis/scleritis	H15
Severe comorbid	Cardiovascular	Aortitis	I79.1
conditions	cardiorespiratory system	Arterial/venous thrombosis	I82
		Cardiac tamponade	I31.9
		Pulmonary haemorrhage	R04.8
		Stroke (cerebral infarction)	I63
		Transient ischaemic attack	G45
	Hepatic and gastrointestinal	Intestinal pseudo-obstruction	K56.0
	Neurological	Acute confusional state/psychosis	F05.1, F05.9
		Aseptic meningitis	G02.0, A87.0, G01
		Cranial neuropathy	S04

¹¹SLE severity and severity algorithms defined in Section 10.3.3.3 [39, 56].

	Group	Conditions	ICD-10 codes

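### Table 20 codes pleuritis entirely with tuberculosis codes, against Tables 17 and 21, and its autoimmune row holds an osteoarthritis code and no rheumatoid arthritis code

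*Protocol*

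**What the plan says.** Table 6 (Section 10.3.3) has a row "Comorbidities relevant for SLE patients (Table 20"), ticked for both the serious infection and the malignancy cohort. The section says that the Table 6 variables will be considered when the propensity score is built.

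Table 20 (Appendix 3) contains two rows of interest:

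- *Pleuritis*, listed under the SLE-specific risk adjustment index and coded "A15.6, A15.7, A16.5, A16.7".
- "Autoimmune diseases excluding SLE (e.g., rheumatological, inflammatory bowel disease and multiple sclerosis"), coded "L40, I73.0, M15.0, M35.0, K50, K51, G35".

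Other parts of the protocol bear on these rows:

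- Table 17, the list of opportunistic serious infections, labels A15 "Respiratory tuberculosis, bacteriologically and histologically confirmed" and A16 "Respiratory tuberculosis, not confirmed bacteriologically or histologically".
- Table 21, used by the severity and activity algorithms, has a row "Pleurisy/pleural effusion" coded J90 and J91.
- Section 10.3.3.1 gives the reason for the autoimmune covariate in the malignancy cohort: "other comorbidities may increase inflammatory status, namely other autoimmune diseases (excluding SLE"). Section 10.3.3.2 names autoimmune disease as a confounder for serious infection and refers to Table 20.
- Section 10.3 adopts the 2019 WHO ICD-10. Appendix 3 calls the lists exemplar and leaves their final form to the SAP.

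**The concern.** A propensity score balances the variables as coded, not as labelled. If pleuritis is defined by tuberculosis codes, matching and the balance table will report on past tuberculosis under the name of a lupus comorbidity. These codes also lie within the A00-B99 range of Table 16, so an infection history enters the model as an SLE manifestation.

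The autoimmune row raises a related problem. A reader of the balance table would take it to cover rheumatological autoimmune disease. As printed, it counts an osteoarthritis code and does not count rheumatoid arthritis. Section 10.7.1.4 adds variables still imbalanced after matching to the outcome model, but that safeguard cannot pick up a disease that was never coded. What is at stake is confounder control in both primary comparisons, and the meaning of two lines in the baseline and balance tables.

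**Working it through.** The protocol gives no figure to reproduce here. The check sets its code lists side by side.

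**Pleuritis**

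| Table 20 code | Heading it falls under | Protocol's label for that heading (Table 17) | Among the Table 21 pleurisy codes (J90, J91)? |
|---|---|---|---|
| A15.6 | A15 | respiratory tuberculosis | no |
| A15.7 | A15 | respiratory tuberculosis | no |
| A16.5 | A16 | respiratory tuberculosis | no |
| A16.7 | A16 | respiratory tuberculosis | no |

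Four of four codes are tuberculosis by the protocol's own labels, and none matches its own pleurisy codes. By contrast, the neighbouring pericarditis row shares I30 between Tables 20 and 21. This part needs nothing outside the protocol.

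**Autoimmune diseases other than SLE**

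The protocol prints no label for the individual codes in this row, so they are read against the ICD-10 that it adopts:

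- L40: psoriasis, including psoriatic arthropathy
- I73.0: Raynaud's syndrome
- M15.0: primary generalised osteoarthritis
- M35.0: sicca (Sjögren's) syndrome
- K50: Crohn's disease
- K51: ulcerative colitis
- G35: multiple sclerosis

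Six of the seven are autoimmune or closely related conditions, and one (M15.0) is not. No M05, M06, M33 or M34 code appears, so rheumatoid arthritis, myositis and systemic sclerosis are not listed.

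**Illustrative size for omitted rheumatoid overlap**

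The protocol gives no prevalence of overlap and no relative risk, so all inputs here are assumptions. With prevalence p1 in the anifrolumab group, p0 in the comparator group and relative risk RR for the outcome, the bias factor on the hazard ratio is approximately

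(1 + p1(RR - 1)) / (1 + p0(RR - 1)).

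- p1 = 0.10, p0 = 0.05, RR = 1.5: 1.050 / 1.025 = 1.024
- p1 = 0.15, p0 = 0.05, RR = 1.5: 1.075 / 1.025 = 1.049

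The same RR is used for both outcomes, with no allowance for adjustment through correlated covariates.

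**The case against.** **The lists are provisional.** Appendix 3 leaves them to the SAP, and the autoimmune label is open-ended. This has force for the omitted codes, since an incomplete exemplar list is close to what a protocol may leave open. It has little force for pleuritis, where printed codes contradict two other printed tables. The amendment described in Section 10.3 is to each source's coding system, and translating a wrong code carries the error into every source.

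**Other covariates cover much of the gap.** Pleurisy is a component of the severity algorithm, and Section 10.3.3.3 says the individual components are considered for the propensity score. Prior SLE treatment from Table 14, including methotrexate, leflunomide, JAK inhibitors and rituximab, may partly stand in for rheumatoid overlap. Both points stand and keep the effect small.

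**M15.0 may be a misreading.** The text copy of Table 20 shows 150.0 for congestive heart failure and 173 for peripheral vascular disease, so a wrong character cannot be excluded. The protocol also prints no label for M15.0. This caveat stands for that code only. The missing M05-M06 and the four tuberculosis codes do not depend on it.

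A reader might infer more than the protocol supports:

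- *Two named confounders measure other diseases.* This is true of pleuritis only, because the autoimmune row is mostly autoimmune and includes Sjögren's syndrome.
- *Every patient's pleuritis value is wrong.* A patient with neither pleurisy nor tuberculosis is coded correctly.
- *True pleuritis scores zero on the index.* No weights or scoring rule are given. The row also says pleuritis, not lupus pleuritis.

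**Conclusion.** The pleuritis row is miscoded. Its four codes are tuberculosis by Table 17, and none agrees with Table 21; this rests on the protocol alone. The autoimmune row is contaminated by one code and incomplete for rheumatological disease. The contamination rests on the adopted ICD-10 and on M15.0 having been read correctly; the absence of M05-M06 can be seen directly.

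Both rows are considered for the propensity scores behind both primary comparisons, but the likely effect is small. The illustrative factor of 1.02 to 1.05 compares with a design hazard ratio of 1.5 (Section 10.5.2). It rests wholly on assumed inputs and ignores the partial adjustment through drug history. Severity is minor. The case for acting is a plain contradiction that is cheap to remove, not a large bias.

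**What to change.** Before the code lists are finalised in the SAP:

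1. In the Table 20 pleuritis row, replace A15.6, A15.7, A16.5 and A16.7 with the Table 21 pleurisy codes J90 and J91, optionally adding R09.1. As these codes already enter as a severity component, state how the overlap between the two covariates is handled.
2. Keep tuberculosis under prior infection. Table 6 has a previous-infection row for the serious infection cohort. The malignancy cohort's infection list (Table 22) has no tuberculosis code, so record whether it is wanted there.
3. In the autoimmune row, check M15.0 against the source file, replace it with M05-M06, and add the other systemic rheumatic autoimmune codes, for example M33-M34.

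The cost is a code-list edit. It needs no new data and no change to the design or the study size.

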10.3.3.3 Potential confounders for both cohorts

SLE disease severity and activity

Disease severity and activity are not directly available in secondary data sources included in this study, since validated indexes that assess disease severity and activity are not systematically used in routine practice and therefore not recorded in most data sources. Thus, this study will use algorithms [39, 56], that have been previously used in other settings, including in one European data source. The algorithms are based on previous use of SLE SOC drugs (Table 14) (including drugs mainly used to manage flares, such as non-steroidal anti-inflammatory drugs [NSAIDs]), SLE-related comorbidities (Table 21) and HRU.

SLE disease severity will be assessed as the highest severity experienced by a patient in the baseline period (12 months prior to index date) and could be categorised in three groups: mild, moderate, and severe [56] if meeting at least one of the criteria depicted in Figure 9 during the baseline period.

The severity algorithm will be used in the selection of the study population (Figure 4). The patients with mild SLE will be excluded. Individual components of the severity algorithm will be considered to create the PS at baseline.

[figure not shown]

Figure 9 SLE disease severity algorithm

(*Patients with mild SLE will be excluded from the study*)

a. SLE-related moderate comorbid manifestations: acute pancreatitis, chorioretinitis, demyelinating syndrome/acute inflammatory demyelinating polyradiculoneuropathy, episcleritis/scleritis, haemolytic anaemia, hepatitis (non-viral), ischaemic necrosis of bone, nephritis, renal impairment other than nephritis or end-stage renal disease, lupus enteritis/colitis, mononeuropathy/polyneuropathy, myelopathy, myocarditis, pericarditis, pleurisy/pleural effusion, pseudotumor cerebri, seizure, uveitis vasculitis (excluding aortitis).

- b. If a severe condition exists, the patient(s) will be moved to the severe category.
- c. Rituximab (including biosimilars).

d. SLE-related severe comorbid manifestations: acute confusional state/psychosis, aortitis, arterial/venous thrombosis, aseptic meningitis, cardiac tamponade, cranial neuropathy, intestinal pseudo-obstruction, end-stage renal disease, optic neuritis, pulmonary haemorrhage, stroke/transient ischaemic attack.

SLE-related comorbid conditions are provided in Table 21.

Abbreviations: IM; intramuscular; IV, intravenous; SLE, systemic lupus erythematosus.

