PASS Protocol Anifrolumab, EMEA/H/C/004975, Serious Infections & Malignancies PASS

SLE disease activity

Periods of increased disease activity could be categorised as mild, moderate, or severe flare [56], if meeting at least one of the criteria depicted in Figure 10. Each component of the activity algorithm will be considered in current study: initiation of any of the drugs described in Figure 10, admission to the emergency department with a SLE-related comorbidity or SLE-related hospitalisation.

SLE activity will be considered among patients that have active SLE (Figure 4). For that, patients will be defined as uncontrolled (i.e., one or more flares in the previous 6 months, regardless of the severity of the flare) if at least one of the components of the algorithm is present: initiation of a new SLE SOC (except biologics), use of NSAIDs or other drugs considered in the management of flares, use of emergency department or hospitalisation due to a SLE-related comorbidity. Additionally, individual components will be used to create the PS at baseline.

[figure not shown]

Figure 10 SLE disease activity algorithm

a. SLE-related moderate manifestations: acute pancreatitis, chorioretinitis, demyelinating syndrome/acute inflammatory demyelinating polyradiculoneuropathy, episcleritis/scleritis, haemolytic anaemia, hepatitis (non-viral), ischaemic necrosis of bone, nephritis, renal impairment other than nephritis or end-stage renal disease, lupus enteritis/colitis, mononeuropathy/polyneuropathy, myelopathy, myocarditis, pericarditis, pleurisy/pleural effusion, pseudotumor cerebri, seizure, uveitis vasculitis (excluding aortitis).

b. SLE-related severe manifestations: acute confusional state/psychosis, aortitis, arterial/venous thrombosis, aseptic meningitis, cardiac tamponade, cranial neuropathy, intestinal pseudo-obstruction, end-stage renal disease, optic neuritis, pulmonary haemorrhage, stroke/ transient ischaemic attack.

Initiation: treatment is considered to be 'initiated' if there were no filled prescriptions for that class of medication in the 60 days prior to the medication fill [39].

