Appendix 3 Exemplar code lists

Code lists will be finalised in the SAP.

Table 14 Drug classes and active substances used in SLE SOC

Drug/Procedure	ATC codes
Antimalarials	
Chloroquine	P01BA01
Hydroxychloroquine	P01BA02
Quinacrine (mepacrine)	P01AX05
Glucocorticoids	
Dexamethasone	H02AB02
Methylprednisolone	H02AB04
Prednisolone	H02AB06
Prednisone	H02AB07
Triamcinolone	H02AB08
Immunosuppressive agents	
Biologic immunosuppressants	
Anifrolumab (drug of interest)	L04AA51
Belimumab	L04AA26
Rituximab (including reference product and biosimilars)	L01FA01
Synthetic immunosuppressants	
Anakinra	L04AC03
Apremilast	L04AA32
Azathioprine	L04AX01
Baricitinib	L04AA37
Cyclophosphamide	L01AA01
Cyclosporine	L04AD01
Leflunomide	L04AA13
Methotrexate	L04AX03
Mycophenolic acid/sodium ¹	L04AA06
Sirolimus	L04AA10
Tacrolimus	L04AD02
Thalidomide	L04AX02
Tofacitinib	L04AA29
Voclosporin	L04AD03
Immunoglobulins	
Immunoglobulin G	J06BA02
Plasmapheresis	
Plasmapheresis (procedure)	B05AX03

	ICD-10 codes
	C00-C96
	D00-D09
Malignancies	
-	
All haematological (malignant	C81-C96
neoplasms of lymphoid,	
haematopoietic and related tissue)	
Leukaemia	C91-95
Lymphoma	C81-88, C96
Hodgkin's lymphoma	C81
Non-Hodgkin's lymphoma	C82-86, C96
	C90
plasma cell neoplasms	
All	C00-13, C15-16, C18-23, C25, C32-34, C45, C50-
	54, C56, C60-62, C64-65, C67, C70-73
Bladder	C67
Breast	C50
Cervix uteri	C53
Endometrium	C54.1
Oesophagus	C15
Gastric	C16
Liver	C22
Lung	C33-34
Oropharynx	C09-10
Larynx	C32
Ovary	C56
Prostate	C61
Renal	C64-65
Thyroid	C73
Vagina	C52
Vulva	C51
All (melanoma and other malignant neoplasms of skin)	C43-C44
	neoplasms of lymphoid, haematopoietic and related tissue) Leukaemia Lymphoma Hodgkin's lymphoma Non-Hodgkin's lymphoma Multiple myeloma and malignant plasma cell neoplasms All Bladder Breast Cervix uteri Endometrium Oesophagus Gastric Liver Lung Oropharynx Larynx Ovary Prostate Renal Thyroid Vagina Vulva All (melanoma and other malignant

Abbreviations: ICD-10, international statistical classification of diseases tenth revision.

	ICD-10 codes
All serious infections (composite)	A00-B99, D73.3, E06.0, E32.1, G00-G02, G04.2, G05-G07, H00.0, H44.0,
[81]	H60.0, H60.1, H60.2, H60.3, H66, H67, H70, I30.1, I40.0, J00-J22, J34.0,
	J36, J38.3, J39.0, J39.1, J44.0, J85, J86, K04.4, K04.6, K04.7, K10.2,
	K11.3, K12.2, K14.0, K57.0, K57.2, K57.4, K57.8, K61, K63.0, K65.0,
	K65.9, L00-L04, L05.0, L08, N10-N12, N13.6, N15.1, N15.9, N30.0,

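### Table 21 does not match the severity and flare lists it is meant to code, or the protocol's other code tables, so some infection and injury codes would count as lupus activity

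*Protocol*

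**What the plan says.** Section 10.3.3.3 gives the algorithm in words. The severe list under Figure 9 (note d) begins "SLE-related severe comorbid manifestations: acute confusional state/psychosis, aortitis, arterial/venous thrombosis, aseptic meningitis, cardiac tamponade, cranial neuropathy" and ends "intestinal pseudo-obstruction, end-stage renal disease, optic neuritis, pulmonary haemorrhage, stroke/transient ischaemic attack". The flare algorithm repeats it under Figure 10 (note b): "SLE-related severe manifestations: acute confusional state/psychosis, aortitis, arterial/venous thrombosis, aseptic meningitis, cardiac tamponade, cranial neuropathy", and so on. End-stage renal disease is the only renal entry. Lesser renal dysfunction is in the moderate lists (note a of each figure) as "renal impairment other than nephritis or end-stage renal disease". Both moderate lists also name uveitis, nephritis and vasculitis.

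The notes to both figures then point to the codes: "SLE-related comorbid conditions are provided in Table 21". Table 21 in Appendix 3 has a severe row for renal failure (N17, N19) beside end-stage renal disease (N18.5). It codes renal impairment as "S37.0, N18 (excl. N18.5", nephritis as N10 and N11, cranial neuropathy as S04, vasculitis as M05.2, and arterial/venous thrombosis as I82.

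The codes are used in three places. Severity is the highest level met in the 12 months before index. Uncontrolled disease means at least one flare in the previous 6 months, and one route to a flare is "use of emergency department or hospitalisation due to a SLE-related comorbidity". Individual components of both algorithms go into the propensity score. Appendix 3 opens with "Code lists will be finalised in the SAP".

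**The concern.** Restriction to uncontrolled, moderate-to-severe SLE, followed by propensity score matching, is the protocol's stated protection against confounding by indication (Section 10.9). That protection depends on the codes identifying lupus manifestations. If a listed code denotes an infection or an injury, a patient with stable lupus can be classed as uncontrolled, and the propensity score balances a variable that does not measure what its name says. If a named manifestation has no usable code, patients who have it are missed by that route.

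Infection codes deserve particular attention because serious infection is itself a primary outcome. The same code should not mark a lupus manifestation in one table and an infection in another.

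**Working it through.** No arithmetic beyond counting applies. The check sets the lists side by side.

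**Counts.** Taking uveitis and vasculitis as separate items, note a names 19 moderate manifestations. Table 21 has 18 moderate rows, and the missing one is uveitis. Note d names 11 severe manifestations. Table 21 splits stroke and transient ischaemic attack into two rows, which would give 12, but it has 13. The extra row is renal failure.

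**Disputed rows.** Code meanings come from the protocol's own tables where those give them. Otherwise they come from the 2019 ICD-10, which Section 10.3 adopts.

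| Item | Figure 9 and 10 notes | Table 21 | Conflict |
|---|---|---|---|
| Renal failure | Severe tier has end-stage disease only; other impairment is moderate | Severe: N17, N19 | Tier mismatch |
| Uveitis | Moderate | No row | Item not coded |
| Nephritis | Moderate | N10, N11 | Table 18 puts N10 under urinary tract infection; Table 16 has N10-N12 as serious infection; Table 20 codes nephritis N00, N01, N03, N05 |
| Renal impairment | Moderate | S37.0 and N18 except N18.5 | S37.0 is kidney injury |
| Cranial neuropathy | Severe | S04 only | S04 is cranial nerve injury |
| Vasculitis, not aortitis | Moderate | M05.2 only | Rheumatoid vasculitis only |
| Arterial/venous thrombosis | Severe | I82 only | Venous part only |

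The first three rows are proved from the protocol alone. The last four need the ICD-10 nomenclature. The nephritis row is the firmest evidence of miscoding: Tables 20 and 21 share no code for the same condition, and both Table 21 codes lie inside the study's serious-infection list.

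**Where each error can act.**

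1. Eligibility by severity. Moderate and severe patients are both admitted (Section 10.2.2.1), so moving N17/N19 between tiers does not change who enters. Footnote 3 of that section expects only a very small group to be moderate or severe through comorbidity without a prescription of SOC for moderate/severe SLE.
2. Uncontrolled disease. A flare of any severity counts, so the tier is again immaterial, but the code is not. An emergency visit or admission for N10, N11, S04 or S37.0 would count as a flare.
3. Propensity score. A miscoded component enters as a covariate with the wrong meaning. The tier of N17/N19 matters here only if components are grouped by tier, which the text does not settle.

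The two cohorts differ for N10/N11. The serious infection cohort excludes patients with a serious infection in the previous 6 months, and an admission coded N10 or N11 meets that definition. Such an admission therefore cannot bring a patient into that cohort as a false flare, though an emergency visit without admission or intravenous antimicrobials still could. The malignancy cohort has no such exclusion.

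**The case against.** The strongest reply is that Table 21 is labelled exemplar and is to be completed in the SAP. That would answer a complaint about missing detail. It does not answer stated content that contradicts Section 10.3.3.3 and three other tables. The planned adaptation to local coding systems would carry the errors forward unless someone corrects them.

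Second, Section 10.9 already concedes that acute manifestations and comorbidities may be hard to separate, with renal impairment as its example, and promises counts of patients meeting each criterion. This stands as disclosure of a general difficulty. It does not cover infection or injury codes standing in for lupus manifestations.

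Third, the table was read by a program and is visibly broken in places; the lupus enteritis row shows no code. The missing uveitis row should be checked against the published table. Figures 9 and 10 are also not visible, so the exact diagnosis rules cannot be confirmed.

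Three stronger readings are tempting, and the documents do not support them:

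- A reader might infer that the renal failure row lets in patients whom the algorithm would exclude. The algorithm already has lesser renal impairment as moderate, so this is mainly a grading conflict with little effect on eligibility.
- A reader might call D55-D59 and G56-G64 wrong as well. They are broad blocks for conditions the algorithm names (haemolytic anaemia, mononeuropathy and polyneuropathy). Narrowing them is a judgement, and removing G56-G57 outright would drop mononeuropathies that the lists include.
- A reader might want a percentage of comparators falsely classed as uncontrolled. The protocol gives neither the flare frequency nor the frequency of these codes, so any figure would be invented. Starting a new non-biologic SOC drug or using NSAIDs also counts as a flare, so many patients would qualify regardless.

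**Conclusion.** The point holds as an internal inconsistency with some clear miscoding. Table 21 has one severe row that the algorithm does not grade as severe and lacks one moderate item. One row (nephritis) contradicts three of the protocol's other tables. Four more rows are wrong or incomplete under the adopted ICD-10: S37.0, S04, M05.2 and I82. Used as written, the table would misassign some flares and some propensity score components.

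The numerical effect cannot be derived from the documents. Its direction between arms is not established either: the same list applies to both. It is plausible that false flares fall more on comparators, who come from all SOC users, but nothing in the protocol measures this. The conclusion assumes that the table text is complete as read and that the ICD-10 meanings are those of the 2019 version. The correction is worth making because it costs almost nothing now and concerns variables on which the comparison depends.

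**What to change.** Before the code lists are finalised, reconcile Table 21 with the notes to Figures 9 and 10 and with Tables 16, 18 and 20:

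- Grade N17/N19 consistently with the figure notes.
- Replace N10, N11 with the nephritis codes of Table 20 (N00, N01, N03, N05).
- Delete S37.0 and replace S04 with codes for cranial nerve disorders (for example within G50-G53, to be confirmed by the coding team).
- Correct the vasculitis row so that it is not limited to rheumatoid vasculitis.
- Add codes for arterial thrombosis (for example I74) and for uveitis (for example H20).
- Consider limiting D55-D59 to acquired forms (D59).

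As a standing check, no code should serve both as a lupus manifestation and as a serious infection without a stated reason. Under that check the aseptic meningitis codes (G01, G02.0, A87.0) also need a decision, because Table 16 contains G00-G02 and A00-B99.

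The cost is a code-list edit, with no new data and no change to the design. The numbers qualifying through a comorbidity may shift slightly, down where codes are removed and up where they are added.
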